5. LIST OF ABBREVIATIONS

[figure not shown]
AE	Adverse event
BBSS	Biberoglu Behrman symptom severity scale
C_{avg}	Average concentration
C_{max}	Maximum concentration
CRF	Case report form
DHEA	Dehydroepiandrosterone
dL	Deciliter
ECG	Electrocardiogram
FSH	Follicle-stimulating hormone
GCP	Good Clinical Practice
GnRH	Gonadotrophin releasing hormone
g	Grams
hCG	Human chorionic gonadotrophin
ICH	International Conference on Harmonization
IGF-1	Insulin-like growth factor-1
IRB	Institutional Review Board
IND	Investigational new drug
IUD	Intra-uterine device
kg	Kilogram(s)
LD ₅₀	Median lethal dose
LH	Luteinizing hormone
m	Meters
mg	Milligram(s)
mL	Milliliter
ng	Nanograms
NRS	Numerical Rating Scale
ODI	Off-Drug Interval
PCOS	Polycystic Ovarian Syndrome
PK	Pharmacokinetic
RBC	Red blood cell
SAE	Serious adverse event
VAS	Visual Analog Scale
WBC	White blood cell

6. BACKGROUND INFORMATION

6.1 Rationale for Current Study

Repros believes telapristone offers the potential to provide significant symptomatic relief to women that suffer from a variety of reproductive disorders in which progesterone may be implicated. Most notably the sponsor has seen significant clinically relevant impact on the symptoms of both uterine fibroids and endometriosis.

[figure not shown]
27AUG2018 Abbreviated CSR ZPE-202

546

FDA Guidance For Liver Enzyme Elevation Characterization as SAE

- 1. LFTs \geq 8 x ULN
- 2. LFTs \geq 5 x ULN for 2 consecutive weeks
- 3. LFTs \geq 3 x ULN + Bilirubin 2 x ULN
- 4. LFTs \geq 3 x ULN + clinical signs or symptoms (nausea; jaundice; etc.)

6.5 Ethical Conduct of the Study

This trial will be conducted in strict compliance with the protocol and all applicable FDA regulations and GCP guidelines to insure Good Clinical Practice standards. The Institutional Review Board (IRB) for this study is IntegReview, [name].

[REDACTED]

7. TRIAL OBJECTIVES AND PURPOSE

The primary objective of this study is to determine the safety and efficacy of two oral doses of Proellex administered to premenopausal women with pelvic pain associated with endometriosis confirmed within the last seven years and using prescription medications for endometriosis pain. Proellex will be administered for up to 3 cycles (18 or 16 weeks in duration), each separated by an Off-Drug Interval (ODI).

8. TRIAL DESIGN

[figure not shown]
8.1 Study Endpoints

Primary Endpoint

- Change and percent change in the individual BBSS scores of the three patient reported outcomes (dysmenorrhea, dyspareunia and non-menstrual pelvic pain) by study visit and treatment cycle

Secondary Endpoints

- Change in daily average use and percent change of prescription analgesics from the baseline menstrual cycle to the matching period leading up to Week 18, the last day of dosing of the first cycle of treatment.
- Change in daily average use and percent change of over the counter analgesics from the baseline menstrual cycle to the matching period leading up to Week 18, the last day of dosing of the first cycle of treatment, calculated based on days with reported values.
- Change in daily average use and percent change of overall medication use, prescription and over the counter, from the baseline menstrual cycle to the matching period leading up to Week 18, the last day of dosing of the first cycle of treatment, calculated based on days with reported values.
- Change and percent change in BBSS score incorporating the two physician-reported scores by study visit and treatment cycle.
- Change and percent change in the individual BBSS scores of the three patient reported outcomes (dysmenorrhea, dyspareunia and non-menstrual pelvic pain) by study visit and treatment cycle.
- Change from baseline in pain assessed using a Visual Analog Scale (VAS) by study visit and treatment cycle.
- Change from baseline in daily average dysmenorrhea and non-menstrual pelvic pain using an 11-point numerical rating scale (NRS) by study visit and treatment cycle.

8.2 Study Design

8.2.1 Overview of Study Design

This study is a phase 2, 3-arm-study with an 18 week active dosing period and an option for subjects to receive 2 additional 16-week cycles of active treatment at their randomized dose (6 mg or 12 mg/day). Placebo subjects who elect additional treatment will receive treatment at 12 mg/day. The treatment dose will remain double-blind. The study will be conducted in 3 stages. In the first stage, women will undergo a baseline assessment period with no treatment. This stage will last as long as it takes to record at least one full menstrual cycle (ovulation until ovulation).

Subjects will be provided with a daily diary with which to record patient reported scores for the three elements of endometriosis pain: dysmenorrhea, non-menstrual pelvic pain and dyspareunia (BBSS).

For stage 2, following the baseline assessment period, at Visit 3, 60 subjects will be randomized into one of 3 arms in a 1-1-1 fashion. The start of dosing should commence as soon as possible after ovulation following the end of the previous menstrual event.

Once the 18 week active dosing period is completed, subjects will be followed until menses has returned (usually within 21 days or less). Subjects may elect to receive up to 2 additional cycles of treatment at their randomized dose (6 mg or 12 mg/day), placebo-treated subjects will receive treatment at 12 mg/day. In stage 3 all subjects will receive active treatment but the treatment dose will remain double-blind. For subjects who do not choose additional treatment cycles, this will be their final follow-up visit. During the follow-up period subjects will continue to record study information in the daily diary.

For stage 3, subjects who are eligible to receive additional cycles of treatment and who elect to continue treatment will be scheduled at 21 ± 2 days after start of bleeding in their first menses after Visit 12 (recovery menses). Subjects will receive 2 cycles of treatment separated by an off-drug interval (ODI), after which they will be

followed until menses has returned. During the follow-up period subjects will continue to record study information in the daily diary. The final follow-up visit will be scheduled after blood flow has stopped.

Subjects who complete at least 28 days after Visit 3 and wish to discontinue treatment due to lack of efficacy will be eligible to start active treatment (stage 3). Subjects who discontinue the study prior to this date will not be eligible for additional treatment.

8.2.2 Study Drug Accountability

The designee assigned by the Principal Investigator at each site will maintain accurate records of receipt of all study drugs, including dates of receipt. Reasons for deviation from the expected dispensing regimen must also be recorded. A Drug Dispensing Form will be provided for this purpose. To satisfy regulatory requirements regarding drug accountability and destruction, the Principal Investigator at each site will return all used, unused, or empty and partially used study medication with dispensing records to the Sponsor for final accountability and disposal, after accountability has been verified by the study monitor.

8.2.3 Randomization and Blinding

All subjects will receive no treatment from Visit 1 until Visit 3. At Visit 3, subjects will be randomized to treatment in Arms 1, 2, or 3. Subjects will be treated with one capsule daily of 6 mg or 12 mg of Proellex, or placebo, which will be administered for 18 weeks. Subjects who elect to receive additional treatment cycles will be treated at their previously randomized dose level. Subjects randomized to placebo treatment will receive treatment at 12 mg/day. In stage 3 all subjects will receive active treatment but the treatment dose will remain double-blind. Each treatment cycle will be separated by an ODI. Blinded treatments kits will be randomized and distributed by the packaging company.

For the statistical analysis at Week 18, only statistical staff will be unblinded once the acute portion of the study database is locked. All clinical operations staff and staff at investigative sites will remain blinded until completion of the study.

8.2.4 Study Medication

All study drugs will be supplied by Repos Therapeutics Inc. Test drug, Proellex, will be [REDACTED] and will be packaged by a clinical supplies contract vendor designated by Repos Therapeutics Inc. The placebo will also be [REDACTED] [REDACTED] and will be packaged by the same clinical supplies contract vendor. Active and matching placebo capsules will be bottled in identical packaging. Each bottle will have a label containing bottle number, number of capsules, expiration date, a statement "Caution: New Drug – Limited by Federal Law (US) to Investigational use" and instructions to take 1 capsule daily in the morning before breakfast. Subjects will take one capsule with approximately 8 ounces of water and study medication should be taken roughly at the same time every day. Subjects will record study medication date and time on subject drug diary cards.

[REDACTED]

Subjects will not be provided with medication medications by Repos Therapeutics Inc.

8.2.5 [REDACTED]

[REDACTED]

8.3 Selection and Withdrawal of Subjects

Subjects for the study will be selected during screening based on the inclusion and exclusion criteria and clinical assessments listed below. Subjects will be discontinued from the study prematurely if:

- Unacceptable adverse events occur considered by the investigator to be associated with use of the study drug
- The subject requests to be withdrawn from the study
- Any of the following occur:
 - ALT or AST >8xULN

- ALT or AST $>5\times$ ULN for more than 2 weeks
- ALT or AST $>3\times$ ULN **and** (TBL $>2\times$ ULN **or** INR >1.5)
- ALT or AST $>3\times$ ULN with the appearance of fatigue, nausea, vomiting, right upper quadrant pain or tenderness, fever, rash and/or eosinophilia ($>5\%$)
- A need arises for concomitant medication prohibited by the protocol
- The Principal Investigator decides that it is in the subject's best interest
- The subject is noncompliant with the protocol
- Any subject who develops an endometrial thickness ≥ 18 mm will undergo endometrial biopsy. The endometrial biopsy will be forwarded to a member of the Expert Panel for expedited review. If the biopsy shows EIN or hyperplasia (per Expert Panel review), subject will be discontinued from the study. If EIN or hyperplasia is diagnosed the sponsor will be notified and subject discontinued from the study. Appropriate follow up treatment will be provided as deemed necessary by the investigator.
- Any subject who experiences heavy bleeding (bleeding intensity of 4 or more per the Daily Diary Card in [Appendix 3](#)) for 7 consecutive days or more will be discontinued from the study. This does not apply if heavy bleeding occurs in the first recovery menses after withdrawal of drug at the end of treatment, or is no heavier than bleeding was prior to treatment.
- Any subject who develops an endometrial thickness ≥ 18 mm and excessive bleeding that requires dilatation and curettage or hysterectomy will be discontinued from the study and undergo endometrial biopsy. Women with such findings will not be eligible for extension of treatment. Appropriate follow up treatment will be provided as deemed necessary by the investigator.
- Subjects with a biopsy that shows clear evidence of neoplasia, as determined by the expert panel, will be discontinued and be ineligible for extension of treatment.
- The decision to withdraw from the study because of an adverse event, including pain from endometriosis or from another condition, is decided by the subject and the investigator or her personal physician. The event, and any treatment should be recorded in the study records.

8.3.1 Inclusion Criteria

Subjects must meet the following criteria:

- Healthy adult females between 18 and 47 years of age (inclusive) prescribed prescription medication or taking a prescription strength dose of over-the-counter medication for endometriosis pain, and with a BBSS score ≥ 7 at screening (assessed over the previous 28

days. [REDACTED]

- Endometriosis diagnosis must have been surgically confirmed within 7 years. A laparoscopic diagnosis is acceptable.
- Subjects must have a history of at least 3 regular menstrual cycles in which symptoms of endometriosis occurred immediately prior to screening
- Normal or abnormal but non-clinically significant transvaginal ultrasound
- History of menstrual events occurring in regular cycles
- Agreement not to attempt to become pregnant during the trial
- Agreement to use alcohol in moderation and to avoid alcohol consumption within 48 hours before each visit
- Ability to complete a daily subject diary and study procedures in compliance with the protocol
- Women of child-bearing potential must be willing to use double-barrier contraception during the study and for 30 days after discontinuation of study medication. Acceptable double-barrier methods are: male condom with spermicide; male condom with diaphragm; diaphragm containing spermicide plus additional intra-vaginal spermicide
- Has a negative pregnancy test at the Screening and Baseline visits, and subsequent study visits
- A Body Mass Index (BMI) between 18 and 39 inclusive
- Is available for all treatment and follow-up visits

8.3.2 Exclusion Criteria

[figure not shown]
Subjects meeting any of the following criteria will be excluded from the study:

[figure not shown]
- Subject is a post-menopausal woman, defined as either; six (6) months or more (immediately prior to screening visit) without a menstrual period, or prior hysterectomy and/or oophorectomy.
- Subject is pregnant or lactating or is attempting or expecting to become pregnant during participation in the study
- Subjects with abnormally high liver enzymes or liver disease. (ALT or AST exceeding 2 x ULN AND total bilirubin exceeding

[figure not shown]
1.5xULN at screening and confirmed on repeat).

[figure not shown]
- Received an investigational drug in the 30 days prior to the screening for this study
- Subject has a history of PCOS
- Concurrent use of any testosterone, progestin, androgen, estrogen, anabolic steroids, DHEA or hormonal products for at least 2 weeks prior to screening and during the study.
- Use of oral contraceptives in the preceding 30 days. Use of Depo-Provera® in the preceding 10 months.
- Use of GnRHAs (e.g. Lupron Depot) within 3 months of the first dose of study drug (Lupron Depot must have a wash-out period of 3 months after the period of duration of the Lupron dose).
- Has an IUD in place.
- Presence of intramural fibroids that impact the endometrial stripe, submucosal fibroids (any size), or endometrial polyps. Subserosal and intramural fibroids with no impact on the endometrial stripe are acceptable.
- Presence of endometrioma(s)
- Present history or condition that causes non-endometriosis related dyspareunia (e.g. vulvar vestibulitis).
- Past or present history of thrombophlebitis or thromboembolic disorders.
- Known or suspected carcinoma of the breast or reproductive organs.
- Known history of abnormal ECG that, in the opinion of the investigator, is clinically significant and will prevent the subject from completing the study, including a QTc of greater than 450 ms.
- Cervical dysplasia classified as Atypical Squamous Cells of Undetermined Significance (ASCUS) associated with high-risk human papilloma virus (HPV) or Low/High Grade Squamous Intraepithelial Lesion (LGSIL or HGSIL).
- History of abnormal endometrial biopsy including the presence of EIN.
- Recent history (within past 6 months) of alcoholism or drug abuse.
- Known active infection with HIV, Hepatitis A, B or C.
- Previous history of auto-immune disease and/or positive antinuclear antigen (ANA).

[figure not shown]
- Endometrial stripe ≥ 18 mm in thickness at Visit 1.
- Subject is currently taking cimetidine or spironolactone.
- Previous use of telapristone acetate or participation in a Repros clinical study
- Clinically significant abnormal findings on screening examination and laboratory assessments or any condition which in the opinion of the investigator would interfere with the participant's ability to comply with the study instructions or endanger the participant if she took part in the study.

[figure not shown]

[figure not shown]

[figure not shown]

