8.3.2 Exclusion Criteria

[figure not shown]
Subjects meeting any of the following criteria will be excluded from the study:

- Subject is a post-menopausal woman, defined as either; six (6) months or more (immediately prior to screening visit) without a menstrual period, or prior hysterectomy and/or oophorectomy.
- Subject is pregnant or lactating or is attempting or expecting to become pregnant [REDACTED]
- [REDACTED]
- Women with abnormally high liver enzymes or liver disease. (ALT or AST exceeding 1.5x ULN AND total bilirubin exceeding 1.5xULN at screening and confirmed on repeat).
- Received an investigational drug in the 30 days prior to the screening for this study
- Women with a history of PCOS
- Concurrent use of any testosterone, progestin, androgen, estrogen, anabolic steroids, DHEA or hormonal products for at least 2 weeks prior to screening and during the study.
- Use of oral contraceptives in the preceding 30 days. Use of Depo-Provera® in the preceding [REDACTED]
- Use of GnRHs (e.g. Lupron Depot) within 3 months of the first dose of study drug (Lupron Depot must have a wash-out period of 3 months after the period of duration of the Lupron dose).

- Has an IUD in place
- Presence of intramural fibroids that impact the endometrial stripe, submucosal fibroids (any size), or endometrial polyps. Subserosal and intramural fibroids with no impact on the endometrial stripe are acceptable.
- Present history or condition that causes non-endometriosis related dyspareunia (e.g. vulvar vestibulitis).
- Past or present history of thrombophlebitis or thromboembolic disorders.
- Known or suspected carcinoma of the breast or reproductive organs.
- History of abnormal ECG that, in the opinion of the investigator, is clinically significant and will prevent the subject from completing the study, including a QTc of greater than 450 ms.
- Cervical dysplasia classified as Atypical Squamous Cells of Undetermined Significance (ASCUS) associated with high-risk human papilloma virus (HPV) or Low/High Grade Squamous Intraepithelial Lesion (LGSIL or HGSIL).
- History of abnormal endometrial biopsy including the presence of EIN.
- Recent history (within past 6 months) of alcoholism or drug abuse.
- Known active infection with HIV, Hepatitis A, B or C.
- Previous history of auto-immune disease and/or positive antinuclear antigen (ANA).
- Endometrial stripe ≥ 18 mm in thickness at Visit 1.
- Women currently taking cimetidine or spironolactone.

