8.3.2 Exclusion Criteria

[figure not shown]
Subjects meeting any of the following criteria will be excluded from the study:

- Subject is a post-menopausal woman, defined as either; six (6) months or more (immediately prior to screening visit) without a menstrual period, or prior hysterectomy and/or oophorectomy.

- Subject is pregnant or lactating or is attempting or expecting to become pregnant [REDACTED]
[REDACTED]
- Women with abnormally high liver enzymes or liver disease. (ALT or AST exceeding 2 x ULN AND total bilirubin exceeding 1.5xULN at screening and confirmed on repeat).
- Received an investigational drug in the 30 days prior to the screening for this study
- Women with a history of PCOS
- Concurrent use of any testosterone, progestin, androgen, estrogen, anabolic steroids, DHEA or hormonal products for at least 2 weeks prior to screening and during the study.
- Use of oral contraceptives in the preceding 30 days. Use of Depo-Provera® in the preceding [REDACTED]
- Use of GnRHAs (e.g. Lupron Depot) within 3 months of the first dose of study drug (Lupron Depot must have a wash-out period of 3 months after the period of duration of the Lupron dose).
- Has an IUD in place
- Presence of intramural fibroids that impact the endometrial stripe, submucosal fibroids (any size), or endometrial polyps. Subserosal and intramural fibroids with no impact on the endometrial stripe are acceptable.
- Presence of endometrioma(s)
- Present history or condition that causes non-endometriosis related dyspareunia (e.g. vulvar vestibulitis).
- Past or present history of thrombophlebitis or thromboembolic disorders.
- Known or suspected carcinoma of the breast or reproductive organs.
- History of abnormal ECG that, in the opinion of the investigator, is clinically significant and will prevent the subject from completing the study, including a QTc of greater than 450 ms.
- Cervical dysplasia classified as Atypical Squamous Cells of Undetermined Significance (ASCUS) associated with high-risk human papilloma virus (HPV) or Low/High Grade Squamous Intraepithelial Lesion (LGSIL or HGSIL).

- History of abnormal endometrial biopsy including the presence of EIN.
- Recent history (within past 6 months) of alcoholism or drug abuse.
- Known active infection with HIV, Hepatitis A, B or C.
- Previous history of auto-immune disease and/or positive antinuclear antigen (ANA).
- Endometrial stripe ≥ 18 mm in thickness at Visit 1.
- Women currently taking cimetidine or spironolactone.

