11.1.2 Definitions

Adverse Event – Any untoward medical occurrence in a clinical investigation subject administered a drug and does not necessarily have a causal relationship with this treatment. An AE can therefore, be any unfavorable and unintended sign (including an abnormal laboratory finding), symptom, or disease temporally associated with the use of an investigational product, whether or not related to the investigational product.

Serious Adverse Event (SAE) – An adverse drug experience that results in any of the following outcomes: death, a life-threatening experience, requires or prolongs subject hospitalization, results in persistent or significant disability/incapacity, or is a congenital anomaly or birth defect.

Cases of liver transaminases that increase above 3 times the upper limit of normal must be reported as SAEs regardless of whether the above defined SAE criteria are met.

Unexpected Adverse Event: Any adverse event that is not identified in nature, severity, or frequency in the current Investigator's Brochure.

Additionally, the Principal Investigator will evaluate all AEs as follows:

Action taken: whether or not the AE caused the subject/patient to discontinue the study medication.

Intensity, to be graded as:

DEGREE	DESCRIPTION
Mild	Awareness of signs and symptoms; easily tolerated
Moderate	Discomfort sufficient to interfere, but not prevent daily activity
Severe	Unable to carry out usual activity

Relationship to study medication, to be graded as:

DEGREE	DESCRIPTION
Definitely	There is evidence of exposure to the study drug, for example, reliable history or acceptable compliance assessment; the temporal sequence of the AE onset relative to the medication is reasonable; the AE is most likely to be explained by the treatment than by another cause; the AE shows a pattern consistent with previous knowledge of the treatment.
Probably	There is evidence of exposure to the study drug; the temporal sequence of the AE onset relative to medication administration is reasonable; the AE is more likely explained by the treatment than by another cause.
Possibly	There is evidence of exposure to the study drug; the temporal sequence of the AE relative to the medication administration is reasonable; the AE could have been due to another equally likely cause.
Probably not	There is evidence of exposure to the study drug; there is another more likely cause of the AE.

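### The numeric liver exclusion requires raised bilirubin as well as raised ALT or AST, so it sets no entry ceiling for an isolated enzyme elevation and contradicts its own lead sentence

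*Protocol*

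**What the plan says.** The liver bullet in Protocol 8.3.2 (latest protocol text) opens with a general statement, "Subjects with abnormally high liver enzymes or liver disease", that carries no bilirubin condition. A bracket then gives the numbers: "ALT or AST exceeding 2 x ULN AND total bilirubin exceeding" 1.5xULN at screening, confirmed on repeat.

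The connector is not a product of text extraction. The original protocol has "ALT or AST exceeding 1.5x ULN AND total bilirubin exceeding 1.5xULN at screening and confirmed on repeat", and later versions, including Amendment 8US, have "ALT or AST exceeding 2 x ULN AND total bilirubin exceeding 1.5xULN at screening and confirmed on repeat". The enzyme threshold moved from 1.5 to 2xULN, but the AND stayed.

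Protocol 8.3 lists four liver reasons for discontinuation. Two act on transaminases alone: "ALT or AST >8xULN", and above 5x "ULN for more than 2 weeks". The other two need a value above 3xULN together with bilirubin above 2xULN or INR above 1.5, or together with symptoms, rash, fever or eosinophilia. The same list lets the investigator withdraw a subject by judgement: "The Principal Investigator decides that it is in the subject's best interest".

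On reporting, 11.1.2 states: "Cases of liver transaminases that increase above 3 times the upper limit of normal must be reported as SAEs". Section 11.1.3 repeats this and starts SAE documentation at informed consent.

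**The concern.** A two-part test joined by AND is narrower than either part. Here it reduces an exclusion for high enzymes or liver disease to one for combined enzyme and bilirubin elevation. A woman with markedly raised ALT and normal bilirubin fits the lead sentence but not the bracket.

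Two things are at stake. The first is safety: this protocol gives liver enzymes special attention, with four stopping rules and a dedicated SAE rule, yet its visible entry rule has no standalone enzyme limit. The second is consistency across sites. A site that takes the bracket as the definition could enrol a woman whom another site, applying the lead sentence, would refuse. With 20 women planned per arm, one such woman is 1/20 = 5% of her arm, and a later liver event in her would be hard to attribute to drug or to baseline.

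**Working it through.** The plan states no figure to reproduce, so the check sets the rules side by side.

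**Rules, in multiples of ULN**

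- Entry bracket (8.3.2): exclude if (ALT or AST > 2) AND (bilirubin > 1.5), confirmed on repeat.
- Numeric stop (8.3): ALT or AST > 8; or > 5 for more than 2 weeks; or > 3 with (bilirubin > 2 or INR > 1.5); or > 3 with listed symptoms or signs.
- Reporting level (11.1.2, 11.1.3): transaminases above 3.
- Amended entry rule: exclude if ALT or AST > 2, confirmed on repeat, at any bilirubin.

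**Case examined:** bilirubin 1.0xULN, INR 1.0, no symptoms, with the enzyme value taken as confirmed.

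| ALT (xULN) | Excluded by bracket | Numeric stop in 8.3 | Above 3xULN | Excluded by amended rule |
|---|---|---|---|---|
| 2.5 | no | no | no | yes |
| 4 | no | no | yes | yes |
| 6.5, for 1 week | no | no | yes | yes |
| 6.5, for 3 weeks | no | yes | yes | yes |
| 9 | no | yes | yes | yes |

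**Reading the table**

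1. The bilirubin part is false at 1.0, so the bracket is false whatever the ALT. The same holds for any bilirubin up to and including 1.5xULN.
2. The bracket passes a woman who already meets a numeric stop in two of the five rows: above 8xULN on a single value, and above 5xULN for more than 2 weeks. The second row assumes that time before randomization counts towards the 2 weeks; 8.3 does not say.
3. At 2.5, 4 and short-lived 6.5xULN, neither the bracket nor a numeric stop acts. For values above 3xULN, symptoms or INR above 1.5 would bring a stop into play, so this gap is confined to asymptomatic women with INR at or below 1.5.
4. Under the amended rule all five rows are excluded, and no confirmed elevation that passes entry meets a numeric stop.

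**Screening cost.** The documents give no prevalence. If a share p of otherwise eligible women had isolated confirmed elevation, the number needed to randomize 60 is 60/(1 − p), rounded up. With p assumed to be 0, 0.02 or 0.05: 60/1 = 60; 60/0.98 = 61.2, so 62; 60/0.95 = 63.2, so 64.

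**The case against.** The strongest reply is that 8.3 closes the worst cases itself. Its discontinuation rules are not limited to values seen on drug. Stage 1 is untreated and lasts at least one full menstrual cycle (8.2.1), and randomization comes only at Visit 3 (8.2.3). A woman with a known ALT above 8xULN can therefore be discontinued before she takes a capsule. This stands. A reader might infer that the protocol contradicts itself outright and would dose such a woman. The documents do not support that: the entry and stopping rules can operate in sequence, and what remains is an incoherence in which a woman passes the bracket while already meeting a reason to leave.

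It is also fair that other text can keep her out: the lead sentence, the requirement in 8.3.1 that subjects be healthy, the last exclusion in 8.3.2 on clinically significant screening findings, and investigator discretion in 8.3. These lower the risk, but none gives a number, so they do not set a common ceiling across sites.

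A reader might treat the 3xULN SAE rule as a limit on dosing. It is a reporting rule, and it speaks of values that increase above that level, which a raised screening value may not have done. At most, reporting from consent could bring the value to the sponsor before Visit 3.

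Section 9 and some figures are not visible, and the stated reasons for Amendment 4 mention LFTs at Visits 1, 6 and 12. A further limit or a retest in Stage 1 cannot be ruled out.

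Finally, a standalone limit of 2xULN reaches below the levels at which 8.3 stops anyone on enzymes alone. Aligning entry with 8.3 alone would remove the overlap with the stopping rules. It would leave the bracket at odds with its lead sentence, and 2xULN is the sponsor's own threshold.

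**Conclusion.** The point holds and should be corrected, with medium confidence. As written, the only visible numeric liver exclusion sets no ALT or AST ceiling when bilirubin is at or below 1.5xULN, against the lead sentence of the same bullet. This is a stated rule that gives the wrong result, not a missing detail.

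The overlap with the numeric stopping rules is limited to isolated elevation above 8xULN, or above 5xULN for more than 2 weeks, and 8.3 may remove those women before dosing. The larger gap is isolated, asymptomatic elevation below those levels with INR at or below 1.5. Between 2 and 5xULN, no visible numeric rule acts at entry or on study; between 5 and 8xULN, none acts until more than 2 weeks have passed. Only unquantified judgement keeps such a woman out.

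This rests on a literal reading of the bracket and on no further limit standing in text that cannot be seen. The documents give no frequency of such women, so no event rate or count of harm is claimed.

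**What to change.** Amend the liver bullet in Protocol 8.3.2 so that ALT or AST above 2xULN, confirmed on repeat, excludes on its own. The medical team should decide whether isolated bilirubin above 1.5xULN also excludes, and write that as a separate condition.

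The cost is one line in the eligibility criteria, by amendment, with no new procedure. A few more screen failures are possible: under the assumed range of 0% to 5%, about 60 to 64 otherwise eligible women would be needed to randomize 60.
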